Section	Original Protocol (12 JUNE 2017)	Amendment 1 (06 SEPTEMBER 2017)	Reason for Change
		event of any delay in obtaining pregnancy test result, subject may be enrolled and randomized if all the other eligibility criteria are met.	

1.0 SYNOPSIS

Name of Sponsor/Company:	Eagle Pharmaceuticals, Inc.
Name of Finished Product:	Ryanodex [®] (EGL-4104) (dantrolene sodium for injectable suspension)
Name of Active Ingredient:	dantrolene sodium
Title of Study:	Phase 2, Multiple-Site, Open-Label, Randomized, 2-Group Parallel Study to Assess the Efficacy and Safety of Ryanodex [®] (EGL-4104) as Adjuvant Treatment in Subjects With Psychostimulant Drug- Induced Toxicity (PDIT).
Protocol No:	EGL-4104-C-1702 – Amendment 1
Principal Investigator:	
Study sites:	Pre-Hospital Emergency Care (PHEC) units in the United States
Study duration	Phase: 2

Psychostimulant-Induced Intoxication (PDIT)

PDIT is a life-threatening condition characterized by sudden onset and fast progression. PDIT occurs secondary to illicit use of psychostimulant drugs (e.g., MDMA, methamphetamine, methylone) for recreational purposes, often taken at mass gathering events where performing intense physical activity in high ambient temperature is commonly observed, such as large music festivals and concerts. The main clinical characteristics of PDIT include core body hyperthermia of >39.5° C (103.1° F) and changes in mental status such as agitation, delusions, hallucinations, seizures or even coma. Other signs and symptoms often include tachycardia, tachypnea, rhabdomyolysis, dehydration, acidosis and hyperkalemia. Current treatment includes cooling measures (e.g. ice packs, evaporative cooling, cold water immersion), sedative agents (e.g. benzodiazepines, ketamine) and supportive measures. Treatment delay often leads to serious complications including cardiac arrhythmias, coagulation disorders and organ dysfunction, which may result in long-term sequelae or even death.

Mass-Gathering Medicine

Hundreds of mass gatherings, including city marathons, parades, concerts, and music festivals, occur throughout the US each year and, in general, they are safe and enjoyable events. However, attendees at these events can be isolated from access to regular emergency services and medical care, and illness, injuries, and fatalities do occur.

Mass gatherings require health and medical services, harm-reduction strategies, operational plans, and emergency contingency plans to be in place. A mass gathering can be defined as any occasion that attracts

sufficient people to strain the planning and resources of the community, city, or nation hosting the event. Massgathering medicine (MGM) is a young and rapidly evolving discipline with ties to emergency medicine, disaster medicine, and public health.

Mass gatherings take place in dynamic environments. Planning and provision of health and emergency medical services is challenging. Patterns of injury and illness differ from those typically encountered in the community. Medical responses are complicated by logistical challenges, such as weather extremes, crowding, site access, geographical barriers and communication difficulties. These unique challenges, along with increased rates of morbidity, mean that baseline 911 emergency services alone are not enough to ensure the safety of attendees. As well, there is a growing awareness of the impact of mass gatherings on local communities and a requirement to avoid compromising baseline emergency services. Consequently, there is a shift away from a standard first-aid model of care and toward on-site multidisciplinary medical teams (e.g., physicians, nurses, paramedics) offering a higher and more complex level of care, which includes similar capabilities as those commonly available at an emergency department of a regular community hospital.

Objectives

Primary: To evaluate the efficacy of Ryanodex[®] for the treatment of PDIT, administered as an adjuvant treatment to the current standard of care (SOC).

Secondary: To evaluate the safety and tolerability of Ryanodex[®] for the treatment of PDIT administered as an adjuvant treatment to current SOC.

Methodology

Study EGL-4104-C-1702 is a phase 2, multiple-site, open-label, randomized, 2-group parallel study of Ryanodex[®] for the treatment of PDIT, administered intravenously (IV) as adjuvant treatment to the current SOC, which is defined as body cooling and supportive measures, including treating related symptoms and any existing comorbidities. Due to the acute and serious nature of PDIT, more commonly occurring in young individuals attending mass gathering events (e.g. large music festivals and concerts), and the importance of early diagnosis and fast implementation of treatment, the study will be conducted at qualified pre-hospital emergency care facilities [PHEC]. The PHECs are medical units fully equipped and staffed to provide adequate emergency medical care to patients with PDIT. This study is designed to evaluate the safety and efficacy of Ryanodex[®] in this acutely ill patient population in an emergency setting, where study subjects are anticipated to be treated over a short period of time and then transferred to another medical facility or released, depending on their overall medical status. In order to standardize subject's evaluation, data collection and subsequent analysis, functioning of each organ system will be assessed individually and will also be conducted using the Logistic Organ Dysfunction System (LODS).

After diagnosis of PDIT, the Investigator should initiate SOC treatment as quickly as possible, and will assess the subject's eligibility for study participation. The Investigator will document subject's baseline status.

Body cooling measures should be stopped at the first instance of rectal temperature hypothermia.

Enrolled study subjects are expected to remain at the study site for a maximum of 6 hours after screening, prior to discharge from the study site. Subjects who require hospitalization beyond for the study after Screening (e.g., because of complications, adverse events [AEs], or other reasons) will complete the required study discharge procedures prior to their continuation of care outside of the study. The Investigator will make all reasonable efforts to obtain subjects' medical data from these medical facilities.

Logistic Organ Dysfunction System

The Logistic Organ Dysfunction System (LODS) provides an objective tool for assessing organ dysfunction in critical patients. The LODS identifies organ dysfunction for 6 organ systems: neurologic, cardiovascular, renal, pulmonary, hematologic and hepatic, taking into account both the relative severity among organ systems and the level of severity within an organ system.

Standard of Care

Implementation of standard of care (SOC) should be initiated as quickly as possible after admission of the subject to the PHEC. For the purpose of this study, SOC is defined as efficient body cooling by physical methods and supportive measures, implemented as following:

Body Cooling

- *Ice packs*: should be placed to neck, axilla, and inguinal regions.
- **Evaporative cooling**: application of water (room temperature) over the body surface, via mist application with continuous use of a fan. Subjects may be covered with a thin sheet. Do not use ice/cold water immersion because of concerns with shivering (which could potentially worsen hyperthermia), and the need for IV access and other monitoring measures and medical procedures.
- **Benzodiazepines**: may be administered to ameliorate shivering induced by cooling methods, as deemed necessary by the Investigator.

Supportive Measures

Randomized subjects will also receive any other medical treatments and/or supportive measures (IV fluids, respiratory support) for the adequate treatment of existing complications or comorbidities (e.g. dehydration, seizures, aggressiveness, asthma) following acceptable medical practice, and as deemed necessary by the Investigator.

Treatment Groups

Upon admission to the PHEC, eligible patients with PDIT will be randomized in a ratio to one of the following treatment groups:

- Group A: Ryanodex[®], as added treatment to SOC
- Group B: SOC only

The Investigator will make all reasonable efforts to perform the **second** drug screen test during the screening process or as soon as feasible after randomization. The **second** drug screen test may not be feasible in some subjects, due to the dehydration, use of oxygen therapy and/or endotracheal intubation commonly seen in patients with PDIT, which may result in dryness of the oral mucosa. A blood sample for testing for the presence of psychostimulant drugs will also be collected after randomization.

Subjects in Group A will receive SOC immediately followed by an initial dose of Ryanodex[®] (study drug) of 2.5 mg/kg administered as an IV bolus. Initial dose of Ryanodex[®] should be administered within minutes of randomization. The goal is to achieve an adequate clinical response, which is defined as meeting both of the following criteria:

2. Logistic Organ Dysfunction System (LODS) score ≤ 5

If the subject is not showing adequate clinical response between 10 and 30 minutes after the initial dose, or the subject had achieved an adequate response but afterwards signs/symptoms believed to be associated with PDIT re-appear a

second IV bolus dose of 2.5 mg/kg of Ryanodex[®] may be administered between 10 and 30 minutes following the initial dose. This repeat dosing is permitted, as deemed necessary by the Investigator, unless the subject demonstrates clinically significant signs/symptoms of dantrolene-related adverse reactions.

The Investigator must clearly record all clinical assessments and symptoms leading to repeat dosing of Ryanodex[®]. The total administered dose of Ryanodex[®] in a 24-hour period should not exceed 10 mg/kg.

Individual Subject Stopping Rules

- The Investigator may consider stopping study drug if the subject demonstrates clinically significant signs/symptoms of dantrolene toxicity, which may include, but are not limited to, the following: increased skeletal muscle weakness; worsening in the state of consciousness (e.g., lethargy, coma); worsening respiratory status, including increased respiratory muscle weakness, vomiting, diarrhea, or crystalluria; providing none of these signs/symptoms are not attributable to PDIT, a comorbid condition (e.g., asthma, epilepsy, pneumonia) or a concomitant medication (e.g., sedatives).
- The Investigator may stop study drug at any time for that subject's well-being if the Investigator believes that the subject has experienced a serious AE (SAE) possibly related to study drug or a clinically significant non-serious AE possibly related to study drug.
- The subject will be withdrawn from the study if a diagnosis had been made for which dantrolene is the SOC (e.g., malignant hyperthermia [MH]), and treatment with commercially available dantrolene should be initiated.
- In case a subject was unable to provide consent at the time of enrollment due to the severity of their condition (in accordance with the provisions in 21 CFR 50.24), once the subject is able to understand the nature of the study and the consenting process or the subject's relative becomes available, the subject or relative will be informed that the subject has been enrolled in a clinical study and has been treated on an emergency basis with either standard of care (SOC) or with SOC plus an investigational drug. If the subject or relative refuses consent, the Investigator will stop study assessments and procedures at that time, withdraw the subject from the study, and will not perform any subsequent study assessments.

Study Phases

The study will include the following phases: Screening/Baseline, Treatment Phase, and Discharge.

Planned number of subjects:	An estimated total of 100 subjects will be enrolled in the study (approximately 50 per group).
Diagnosis and main criteria for inclusion:	 Male or non-pregnant female subjects, aged 18 years or older, will be eligible for entry into this study if they are diagnosed with PDIT, as evidenced by all the following at Screening: Core body temperature obtained rectally
	 of >39.5° C (103.1° F). LODS score ≥ 6. In the event of any delay in obtaining the lab results for baseline LODS score determination, subject may be enrolled and randomized if all the other eligibility criteria are met; after enrollment if the pending baseline LODS score turns out to be < 6, subject will be withdrawn from the study and

	subsequently replaced with a new subject
	 Known or suspected recent use of a psychostimulant drug, in the judgement of the investigator.
	• Negative pregnancy test for female subjects. If positive, female subjects must be excluded from participating in the study. In the event of any delay in obtaining pregnancy result, subject may be enrolled and randomized if all other eligibility criteria are met. However, female subjects randomized to Treatment Group A (Ryanodex as adjuvant treatment to SOC) must not be dosed with Ryanodex until a negative result of the pregnancy test is available. If a positive pregnancy test is noted after randomization, subject will be withdrawn from the study and subsequently replaced with a new subject to complete the ITT population.
Main criteria for exclusion:	A subject diagnosed with PDIT will be excluded from entering the study if he or she presents with or, in the judgment of the Investigator, meets any of the following criteria at Screening:
	• Diagnosed with or is suspected to have an acute clinically severe infection, which in the opinion of the Investigator may increase the subject's risk for participating in the study and/or may impair the ability of performing and/or interpreting study assessments.
	• Severe hyperthermia secondary to a condition other than PDIT (e.g., thyrotoxicosis, pheochromocytoma, or brain hemorrhage).
	• Likelihood of head trauma in the past 3 months, or other systemic disease that might increase the subject's risk for participating in the study and/or may impair the ability of performing and/or interpreting study assessments.
	• Positive pregnancy test or evidence of active lactation.
	 Known history of allergy or hypersensitivity to dantrolene.
	 Known history of seizure disorders or epilepsy.

	• Current or prior use (within the past 2
Test product, dose, and mode of administration:	Ryanodex [®] : dantrolene sodium for injectable suspension; 250 mg/vial to be reconstituted in 5 mL of sterile water for injection (without a bacteriostatic agent) to yield a 50 mg/mL suspension; to be administered as a rapid IV push of 2.5 mg/kg.
Reference therapy, dose, and mode of administration:	 Standard of Care (SOC): all subjects in both treatment groups will receive SOC. Supportive Measures: all subjects should receive adequate supportive measures for treating PDIT, as well as medically acceptable treatment for complications and comorbidities.

Endpoints:

Primary Efficacy Endpoint:

The primary efficacy endpoint for this study is proportion of subjects achieved a total LODS score \leq 5 at or prior to 60 minutes post-randomization.

Secondary Efficacy Endpoints:

• Proportion of subjects who achieved a LODS total score ≤ 5 at planned time points.

Dantrolene plasma concentration:

Plasma sample data will be presented for all subjects with informed consent and/or summarized.

Safety Assessments:

- Adverse events (AEs)
- Vital signs (blood pressure, respiratory rate, and pulse)
- Clinical safety laboratory tests (hematology and coagulation parameters, and blood chemistry)
- Electrocardiogram (ECG)

- Physical examination
- Brief neurological examination
- Oxygen saturation (measured with pulse oximeter)
- End-tidal CO₂ (ETCO₂)

Sample size:

A planned sample size of 100 (50 per treatment group) fully eligible (for efficacy) subjects are planned to be randomized in this study.

Baseline:

Baseline body temperature will be the first rectal temperature $>39.5^{\circ}$ C (103.1° F) taken during the Screening Phase. Baseline results for other study assessments will be the value closest in time to the baseline rectal temperature and prior to randomization. The SAP may specify additional data handling rules.

Analysis populations:

The Intent-to-Treat (ITT) population is defined as all randomized subjects whose screening test results for presence of a psychostimulant drug was confirmed by blood test. The ITT population will be used as the primary efficacy population.

The Modified Intent-to-Treat (MITT) population is a subset of the ITT population excluding the subjects who are intubated or with mechanical ventilation or CPAP.

The Per Protocol population (PP) is defined as all ITT subjects who met all inclusion/exclusion criteria, have a baseline and at least 1 post-baseline LODS score, and have no major protocol deviations that could affect the efficacy assessments.

The Safety population is defined as all randomized subjects who received any study treatment (SOC only or SOC with Ryanodex[®]). The Safety population will be used to analyze all safety endpoints using actual treatment received.

Efficacy Analysis: The primary analyses of the primary and secondary efficacy endpoints will be conducted on the ITT population. The MITT and PP population analyses of primary and secondary endpoints will be considered supportive.

Safety Population will be used for the safety analysis. No modeling or inferential statistics will be conducted on the safety assessments.

Eagle Pharmaceuticals, Inc. Protocol EGL-4104-C-1702 Amendment 1

Table 1: Schedule of Assessments

Abbreviations: CCM = continuous cardiac monitoring; ETCO₂ = end-tidal carbon dioxide; ECG = electrocardiogram; med = medication; min = minutes; PT = prothrombin time

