## 8.11.3 Concomitant Medications/Therapies

## 8.11.4 Efficacy Analyses

## 8.11.4.1 Primary Analysis

The primary analysis will be conducted on the Intent-to-treat (ITT) population.

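### The blood test that admits subjects to the primary efficacy population is sampled after open-label randomisation, so refusal of consent before the draw can make membership depend on arm and outcome

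*Protocol*

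**What the plan says.** - **Timing of the sample.** Protocol 1.0 Synopsis, Treatment Groups: "A blood sample for testing for the presence of psychostimulant drugs will also be collected after randomization". The readable text gives no latest time.
- **Use of the result.** Under Analysis populations, the ITT population is "all randomized subjects whose screening test results for presence of a psychostimulant drug was confirmed by blood test". The synopsis adds: "The ITT population will be used as the primary efficacy population". SAP section 8.11.4.1 agrees: "The primary analysis will be conducted on the Intent-to-treat (ITT) population". The ITT definition in SAP section 8.8.1 is blacked out.
- **Consent.** For subjects enrolled under the emergency exception, the Individual Subject Stopping Rules say: "If the subject or relative refuses consent, the Investigator will stop study assessments and procedures at that time". The subject is then withdrawn.
- **Baseline blood.** The inclusion criteria show that baseline LODS needs laboratory results: "In the event of any delay in obtaining the lab results for baseline LODS score determination, subject may be enrolled and randomized". Under Baseline: "Baseline results for other study assessments will be the value closest in time to the baseline rectal temperature and prior to randomization". SAP section 8.7 has the same rule.
- **Setting.** SAP section 8.5 confirms that nobody is blinded. The Methodology part of the synopsis expects a stay of at most 6 hours from screening.

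**The concern.** A status that defines the primary population should be fixed before allocation can influence it. Here it depends on a sample taken once the arm is known and, in Group A, possibly once treatment has begun.

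The clearest route to bias is consent. A subject enrolled without consent is told of the trial on becoming able to understand it, or a relative is told on becoming available. If either refuses before the draw, there is no blood result and the subject drops out of ITT. A subject who recovers sooner can refuse sooner. Recovery is close to the endpoint itself, since LODS has a neurologic component and is scored at 60 minutes or earlier. The person deciding also learns that an investigational drug may be involved. Loss from ITT can therefore be linked to both arm and outcome, and the primary comparison would then not be fully protected by randomisation.

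Falling drug levels in a late sample are a possible second route, but the documents do not establish it.

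**Working it through.** **1. The plan's own figure.** SAP section 8.3 gives 50 subjects per arm, two-sided type I error 0.05 and more than 90% power. Both response rates are blacked out, so the figure cannot be reproduced. Run backwards (two proportions, normal approximation, pooled variance, no continuity correction), 50 per arm gives 90% power for a difference of about 27 to 32 points over control rates of 10% to 60%; for example, 40% against 71.6%. This serves only as a scale for what follows.

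**2. Order of events.**
- Randomisation makes the arm known. Group A dosing is meant to follow within minutes.
- The psychostimulant sample comes at some point after randomisation.
- Refusal of consent may come before or after that sample. If before, no sample is taken.
- Membership of ITT needs the blood result.

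So whether a subject is in the primary set can depend on events after allocation. Baseline LODS values, by contrast, must precede randomisation, and only their laboratory results may arrive late. That implies, though no sentence states it, a blood draw before randomisation from which the drug sample could come.

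**3. Illustration with no treatment effect.** All exclusion rates are assumed. Let p be the true response rate in both arms, and let u_R and u_N be the unconfirmed fractions among responders and non-responders.

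Analysed rate = p(1 − u_R) / [p(1 − u_R) + (1 − p)(1 − u_N)], with p = 0.40.
- Group B, 5% unconfirmed in both outcome groups: 0.38 / (0.38 + 0.57) = 40.0%.
- Group A, 15% of non-responders and 5% of responders unconfirmed: 0.38 / (0.38 + 0.51) = 42.7%.
- Group A, 15% of responders and 5% of non-responders unconfirmed: 0.34 / (0.34 + 0.57) = 37.4%.

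The shift is +2.7 or −2.6 points.

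**4. Scale.** The standard error of the difference at 50 per arm is √(2 × 0.4 × 0.6 / 50) = 0.098, or about 10 points. The primary test is blacked out, so I assumed a pooled two-proportion z-test and enumerated it exactly over the number excluded. Overall exclusion in Group A is 0.4 × 0.05 + 0.6 × 0.15 = 11% in the non-responder case and 0.4 × 0.15 + 0.6 × 0.05 = 9% in the responder case; in Group B it is 5%.

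| Unconfirmed pattern | Two-sided rejection | False positives favouring Group A |
|---|---|---|
| 5% everywhere | 5.1% | 2.5% |
| 15% of Group A non-responders | 5.9% | 4.6% |
| 15% of Group A responders | 5.9% | 1.3% |

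**5. Extreme case, also assumed.** Only Group A non-responders are lost. Losing 5 of 50 gives 20/45 = 44.4%, a spurious 4.4 points and rejection of 0.069. Losing 10 gives 20/40 = 50.0%, a spurious 10.0 points and 0.163. With no loss it is 0.052.

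**6. Check of the remedy.** If exclusion does not depend on arm or outcome, losing 5 of 50 in each arm at a 40% rate gives rejection of 0.049, close to nominal.

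**The case against.** **Missing text.** The body of the schedule of assessments is not in the readable text, and neighbouring sentences have gaps. A sampling window may be stated there. This stands, and nobody should infer that the plan has no window. But a window after randomisation, however short, would still leave the arm known at sampling.

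**Clearance.** A reader might infer that late samples will turn true cases negative, using the 6-hour stay as the sampling time. The documents do not support that. They give no half-life, assay limit or arm difference in clearance, and the 6 hours bounds the stay, not the draw. The test is for presence, so a lower level is not in itself a negative result. Nor does anything suggest that study drug alters the assay.

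**Consent is a narrow route.** It needs refusal before the draw. A relative's refusal need not follow recovery, and an early refuser may lack a 60-minute LODS anyway, which an earlier tube would not repair. All of this stands. It limits the size of the problem and is one reason for an analysis of all randomised subjects.

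**Size.** The 15% and 5% are assumptions, and 2.7 points is small against a standard error near 10. This also stands.

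**The pre-randomisation draw is inferred.** The baseline rule selects values and does not schedule a draw. The inference is fair but should be confirmed against the schedule.

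**Conclusion.** The point holds as a weakness in a stated rule. Membership of the primary efficacy set rests on a sample taken after open-label randomisation, and refusal of consent before the draw removes a subject from that set in a way that can depend on arm and outcome.

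Its size and direction cannot be derived. The illustrations run from about 2.7 points either way (15% against 5% non-confirmation in one outcome group) to 10 points in the extreme case of 10 lost non-responders, all at an assumed common 40% response rate. They show what is possible and do not predict a bias towards Ryanodex. Drug clearance remains only a possible secondary route.

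This is a low-cost improvement worth making. It does not show that the primary result would be invalid.

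**What to change.** In the Treatment Groups part of the synopsis, and wherever the schedule repeats it:

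1. State that the psychostimulant sample is an extra tube or aliquot from the baseline LODS blood draw before randomisation. Let the result be pending, so that neither randomisation nor treatment is delayed.
2. If that draw is missed, take the sample within one short fixed window after randomisation, identical in both arms. Do not tie it to dosing: the synopsis makes the Group A dose wait for a pregnancy result in some women, so timing could again differ by arm.
3. Record the clock time, and use only the earliest sample to decide membership.
4. Say how missing, refused and unconfirmed results are classified. The definition also presupposes a screening result to confirm, yet the synopsis says the second drug screen "test may not be feasible in some subjects, due to the dehydration, use of oxygen therapy and/or endotracheal intubation".
5. Add a sensitivity analysis of all randomised subjects, with a stated rule for missing LODS. Earlier sampling alone does not resolve missing or unconfirmed results.

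**Cost.** A change to protocol, laboratory manual and SAP wording, and one extra tube at a busy moment, to be covered by the emergency-consent provisions. No added patients. If the inferred baseline draw is confirmed, no added venepuncture either.

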## 8.7.1 Data to Be Analyzed

will analyze the study data. Data handling will be the responsibility of **1**. The data will be inspected for inconsistencies by performing validation checks.

All data collected during the study will be reported. All details regarding the statistical analysis and the preparation of tables, listings, and figures will be described in the SAP prepared by and approved by the Sponsor before database lock. The statistical analysis will be

performed by

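### Refusal at the deferred-consent talk ends all study assessments with no separate records-only choice, so later safety data, and any primary outcome not yet recorded, can be lost in relation to recovery

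*Protocol*

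**What the plan says.** The rule is in the Protocol, 1.0 Synopsis, last bullet of Individual Subject Stopping Rules. For subjects who could not consent at enrolment, the talk is held "once the subject is able to understand the nature of the study and the consenting process or the subject's relative becomes available". Refusal by either party has a single consequence: the site "will stop study assessments and procedures at that time, withdraw the subject from the study, and will not perform any subsequent study assessments".

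Other provisions that bear on it:

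- **Primary endpoint** (Synopsis, Endpoints; SAP 8.2.1.1): a total LODS of 5 or less "at or prior to 60 minutes post-randomization".
- **LODS content** (Synopsis): "The LODS identifies organ dysfunction for 6 organ systems: neurologic, cardiovascular, renal, pulmonary, hematologic and hepatic".
- **Primary population** (Synopsis, Analysis populations): "all randomized subjects whose screening test results for presence of a psychostimulant drug was confirmed by blood test". Refusers are not excluded. The matching definition in SAP 8.8.1 is blacked out.
- **Data already collected** (SAP 8.7.1): "All data collected during the study will be reported".
- **Missing data** (SAP 8.10): the methods are left to a separate SAP, which is not among the documents.
- **Replacement** (Synopsis, inclusion criteria): withdrawals for a low baseline LODS or a positive pregnancy test are replaced. Nothing is said about refusers.
- **Outside records** (Synopsis, Methodology): efforts to obtain them are described for subjects who go on to hospital, not for refusers.

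**The concern.** One of the two triggers for the talk is the return of capacity. That is neurologic recovery, and the neurologic domain is part of the primary score, so the moment at which a subject can leave the study is linked to the outcome being measured. LODS also needs laboratory values, and the inclusion criteria themselves foresee delay in obtaining them for the baseline score. A subject could therefore be clear-headed enough to refuse before a total of 5 or less is on record. If the drug speeds recovery, Group A may reach this point sooner. The study is open-label (SAP 8.5), so willingness to continue may also differ by arm.

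The safety loss does not depend on the 60-minute window. Subjects may stay on site for up to 6 hours after screening. A dosed subject who refuses remains in the Safety population, and so in the denominator, without study assessment for the rest of that stay. Safety and tolerability are the secondary objective.

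**Working it through.** **1. The plan's own figure.** SAP 8.3 gives 50 per group, two-sided alpha 0.05 and more than 90% power. The response rates and the required number per group are blacked out, so this can be neither reproduced nor refuted. An assumed 72% v 40% needs 49 per group for 90% power and so is compatible with the plan; 62% v 30% also needs 49.

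Power = Φ[(d − 1.96·SE0)/SE1], with SE0 from the pooled proportion and SE1 from the separate ones. For 72% v 40% and n = 50: SE0 = √(0.56·0.44·2/50) = 0.0993; SE1 = √((0.72·0.28 + 0.40·0.60)/50) = 0.0940; (0.32 − 0.1946)/0.0940 = 1.33; power 90.9%.

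**2. When a primary outcome is actually lost.** Four things must coincide: enrolment without consent; a talk within 60 minutes of randomization; a refusal; and no LODS of 5 or less recorded by then. If any one fails, the primary analysis is untouched.

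**3. Illustration: responders refuse before being scored.** Let r be the assumed share of responders lost in an arm with true response p. Counted as failures, the observed rate is p(1 − r) on 50. Excluded, it is p(1 − r)/(1 − pr) on 50(1 − pr). With 72% v 40%:

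| Lost, A / B | Subjects lost, A / B | Counted as failures | Power | Excluded | Power |
|---|---|---|---|---|---|
| 0 / 0 | 0 / 0 | 72.0 v 40.0 | 90.9% | 72.0 v 40.0 | 90.9% |
| 5% / 5% | 1.8 / 1.0 | 68.4 v 38.0 | 87.3% | 71.0 v 38.8 | 90.3% |
| 10% / 10% | 3.6 / 2.0 | 64.8 v 36.0 | 83.2% | 69.8 v 37.5 | 89.6% |
| 15% / 5% | 5.4 / 1.0 | 61.2 v 38.0 | 64.4% | 68.6 v 38.8 | 83.5% |

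With 62% v 30% (power 90.7% with no loss), 10% lost in both arms gives 84.3% as failures and 88.9% excluded. Equal loss costs little if refusers are excluded. The large fall needs both a threefold difference between arms and a rule counting refusers as failures; the documents state neither.

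**4. Direction.** Take no true effect and 40% response in both arms.

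- *Recovering subjects refuse*, 20% of responders in A and 10% in B: as failures, 0.40·0.80 − 0.40·0.90 = −4.0 points; excluded, 0.32/0.92 − 0.36/0.96 = −2.7 points.
- *Relatives refuse for subjects still ill*, 20% of non-responders in A and 10% in B: as failures, no bias; excluded, 0.40/(0.40 + 0.60·0.80) − 0.40/(0.40 + 0.60·0.90) = 0.455 − 0.426 = +2.9 points.

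The sign depends on who refuses and on the analysis rule.

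**5. A bound without response rates.** With k refusers per arm of unknown outcome, the range from worst to best case for the risk difference widens by 2k/50: 4 points for k = 1, 12 for k = 3, 20 for k = 5.

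**The case against.** The strongest reply is that the text says less than it may seem to. It stops study assessments from the moment of refusal; it is silent on records that routine care produces, rather than barring them. The protocol supplied is essentially the synopsis, consent pages were removed, and a fuller withdrawal rule may exist elsewhere. What the cited emergency-consent regulation allows is not in the documents. All of this stands. It limits the finding to the rule as supplied, which has a single outcome and no second choice.

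A reader might infer that primary outcomes are lost as a matter of course. The documents do not support this. Success counts at any time up to 60 minutes, and a subject alert enough for a consent talk may already have been scored. Earlier data are not said to be dropped. Nothing shows that talks within the hour, in severely ill and possibly sedated subjects, are common.

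A reader might also infer a bias against Ryanodex. That does not follow either, because the relative's route need not track recovery and can push the other way.

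Finally, the remedy may not rescue every endpoint value: if blood is not drawn after refusal, routine records may lack LODS components. That also stands. The gain is surest for safety data.

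**Conclusion.** The point holds in limited form. Under the rule as supplied, study safety observation of dosed subjects stops at refusal, and no records-only choice is offered. A primary outcome can be missing in relation to recovery, but only after a refusal within 60 minutes that precedes a qualifying score. The documents give no refusal rate, no timing and no unredacted response rates, so size and direction are unknown. The power figures above rest on assumed response and refusal rates and range from almost no loss (89.6% to 90.3%, equal loss, refusers excluded) to a marked one (64.4%, 15% v 5%, refusers as failures). With no early refusals the effect on the primary analysis is zero. This is a worthwhile, inexpensive improvement to a stated rule; it does not show that the primary analysis is compromised.

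**What to change.** In the deferred-consent bullet, split refusal into two questions: (a) whether further study procedures may be done, and (b) whether data that routine care generates anyway (vital signs, available laboratory results, adverse events, discharge or hospital record) may still be collected. Only refusal of (b) ends data collection. This is subject to ethics-committee and regulatory acceptance.

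In the analysis plan:

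- State that data up to refusal stay in the ITT and Safety analyses.
- Record the time, source (subject or relative), arm and last LODS of each refusal, and report them by arm.
- Pre-specify how refusers with no 60-minute outcome are handled, with best-case and worst-case sensitivity analyses.

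The cost is protocol and consent-form wording with the associated ethics review, and a slightly longer talk. No visits or procedures are added. Routine records may not contain every LODS component, so some endpoint values may remain missing.
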